13.3 Appendix: Expected Normal Ranges in School-Age Children and Adolescents

Table 13-5 Expected Normal Ranges for Heart Rate and Respiratory Rate in School-Age Children and Adolescents

Population	Respiratory Rate (breaths per minute)	Heart Rate (beats per minute)
School-age children (6 to 12 years of age; 20 to 42 kg)	18-30	60-140
Adolescents (13 years of age or older; and/or >42 kg)	12-16	50-100

Source: Adapted from ACLS 2021.

MAAE	medically attended adverse event
MAD	mucosal atomization device
MedDRA	Medical Dictionary for Regulatory Activities
OTC	over the counter
PBMC	peripheral blood mononuclear cell
PCR	polymerase chain reaction
PRN	pertactin
PT	pertussis toxin
PT	preferred term
RRR	reduction of relative risk
SAE	serious adverse event
SAP	statistical analysis plan
S-IgA	secretory immunoglobulin A
SMC	safety monitoring committee
SOC	system organ class

SUSAR	suspected unexpected serious adverse reaction
Tdap	tetanus toxoid, reduced diphtheria toxoid, and acellular pertussis
WCE	whole cell extract
wP	whole cell pertussis

1. Introduction

This statistical analysis plan (SAP) describes the analyses and data presentations for ILiAD's protocol IB-201P "A Phase 2b, Multi-Center, Placebo-Controlled, Randomized Study of BPZE1 Intranasal Pertussis Vaccine in Healthy School-Age Children to Assess the Immunological Response and Safety Profile of a Single Dose BPZE1 With and Without Co-Administration of Tetanus, Diphtheria, and Acellular Pertussis (Boostrix™)" which was issued on 03FEB2021 (amended 02APR2021, 09JUN2021, 07JUL2021, 16AUG2021, 30MAY2022, and 30MAR2023 (still in use in countries outside Costa Rica), 10OCT2023 (applicable in Costa Rica only)). It contains definitions of analysis populations, derived variables, and statistical methods for the analysis of immunogenicity, colonization (substudy only) and safety.

These analyses include one (1) interim analysis and one final analysis. The purpose of the SAP is to ensure the credibility of the study findings by pre-specifying the statistical approaches to the analysis of study data prior to database lock and any data analysis for the interim/final analyses. This SAP is to be interpreted in conjunction with the protocol. Should the SAP and protocol be inconsistent with respect to the planned analyses, the language of the SAP is governing. This SAP will be finalized and signed prior to the clinical database lock for the interim analyses. If the final clinical study report (CSR) contains changes to any planned statistical analyses, the justification for any such differences will be fully documented in the CSR. All statistical analyses detailed in this SAP will be conducted using SAS® Version 9.4 or higher.

2. Objectives

2.1. Primary Objectives

Immunogenicity

- To demonstrate BPZE1 induction of broad pertussis mucosal secretory immunoglobulin A (S-IgA) immunity is measurable at Day 29 by geometric mean fold rise (GMFR) by antibodies to whole cell extract (WCE) (BPZE1, BPZE1 + Boostrix).

Safety

- To assess reactogenicity by toxicity scoring through 7 days following first study vaccination with any combination of pertussis-containing vaccines (BPZE1, BPZE1 + Boostrix, Boostrix).

2.2. Secondary Objectives

2.2.1. Key Secondary Objective

- To demonstrate non-interference of immunoglobulin G (IgG) serum responses for all Boostrix-containing antigens (diphtheria, tetanus, pertussis toxin [PT], filamentous hemagglutinin [FHA], pertactin [PRN]) at Day 29 when BPZE1 is co-administered with Boostrix (BPZE1 + Boostrix vs Boostrix).

2.2.2. Colonization (Optional Substudy Only)

- To describe colonization in each of the groups: BPZE1, BPZE1 + Boostrix, BPZE1 and BPZE1 + Boostrix, Boostrix control.

2.2.3. Mucosal Secretory Immunogenicity (S-IgA)

- To demonstrate BPZE1 induction of mucosal S-IgA immunity is non-inferior to Boostrix at Day 29 as measured by antibodies to WCE (BPZE1 vs Boostrix).
- To demonstrate BPZE1 induction of mucosal S-IgA immunity is greater than baseline at Day 29 (BPZE1, BPZE1 + Boostrix).
- To demonstrate BPZE1 induction of mucosal S-IgA immunity remains greater than baseline over the study period and at Day 169/end of study (EOS) (BPZE1, BPZE1 + Boostrix).
- To demonstrate BPZE1 + Boostrix induction of mucosal S-IgA immunity is non-inferior to BPZE1 at Days 29 and 169/EOS (BPZE1 + Boostrix vs BPZE1).
- To assess if age, time since last aP vaccination (prior to study entry), or other baseline demographics have a differential response to induction of mucosal S-IgA immunity (BPZE1, BPZE1 + Boostrix) at Day 29.
- To assess if baseline antibody values, by baseline quantile, have variable responses at Day 29 to induction of S-IgA immunity when BPZE1 is given alone or with Boostrix (BPZE1, BPZE1 + Boostrix).
- To assess seroconversion for each of the anti-pertussis S-IgA antibodies at Day 29 (BPZE1, BPZE1 + Boostrix, Boostrix). Additional combinations of antibody response (WCE, PT, FHA, PRN, other) may also be tested.
- To assess reverse cumulative distribution curves for S-IgA at Day 29.

2.2.4. Serum Immunogenicity (IgA and IgG)

- To demonstrate that BPZE1 (BPZE1, BPZE1 + Boostrix) induction of serum immunity is significantly greater than baseline at Day 29.
- To demonstrate that BPZE1 + Boostrix induction of serum immunity is non-inferior compared to Boostrix at Day 29 (BPZE1 + Boostrix vs Boostrix).
- To demonstrate that BPZE1 (BPZE1, BPZE1 + Boostrix) induction of serum immunity remains significantly greater than baseline over the course of the study and at Day 169/EOS and to assess antibody decay curves for BPZE1, BPZE1 + Boostrix and Boostrix.
- To demonstrate that BPZE1 induction of serum IgA is non-inferior to Boostrix at Day 169/EOS (BPZE1 vs Boostrix; BPZE1 + Boostrix vs Boostrix)
- To assess if age, time since last aP vaccination (prior to study entry), or other baseline demographics have a differential response to BPZE1 or Boostrix at Day 29 (BPZE1, BPZE1 + Boostrix, Boostrix).
- To assess if baseline antibody values, by baseline quantile, have variable serum immunity responses at Day 29 when BPZE1 is given alone or with Boostrix or Boostrix alone (BPZE1, BPZE1 + Boostrix, Boostrix).
- To demonstrate that BPZE1 (BPZE1, BPZE1 + Boostrix) induces a measurable functional antibody response (subset of subjects) at Day 29; and to assess whether there is similar magnitude as that seen with Boostrix (BPZE1 vs BPZE1 + Boostrix vs Boostrix).
- To assess for seroconversion at Days 29 and 85 (BPZE1, BPZE1 + Boostrix, Boostrix). Additional combinations of antibody response (WCE, PT, FHA, PRN) may also be tested.

- To assess reverse cumulative distribution curves for immune responses (IgA and IgG) at Day 29.

2.2.5. Safety

NOTE: Subjects participating in the substudy will be evaluated for safety endpoints in a separate evaluation after Day 85 re-vaccination/attenuated challenge.

- To describe reactogenicity events during the 7 days following any study vaccination. Primary and re-vaccination/attenuated challenge (substudy subjects) to be described separately, by treatment group. Reactogenicity will be classified by local, nasal/respiratory, and systemic.
- To describe (severity and relationship to study vaccination) all adverse events (AEs) through 28 days following any study vaccination. Primary and re-vaccination/attenuated challenge (substudy subjects) to be described separately and by treatment group.
- To describe (severity and relationship to study vaccination) any medically attended AE (MAAE) through 84 days following any study vaccination. Primary and re-vaccination/attenuated challenge to be described separately and by treatment group.
- To describe any AE of special interest (AESI) and SAE through Day 169/EOS including relationship to study vaccination.
- To describe any severe acute respiratory syndrome coronavirus 2 (SARS-CoV-2) infection or AESI associated with COVID-19 disease if the COVID-19 pandemic remains ongoing in the region or if there are mass vaccinations using a COVID-19 vaccine during study conduct.
- To assess proportion of subjects (subset of subjects) cleared from colonization (present/absent) through Day 85.

2.3. Exploratory Objectives

2.3.1. Mucosal Secretory Immunogenicity (S-IgA) (Optional Substudy Only)

- To evaluate mucosal immunity of individual and combinations of pertussis antibodies (eg, WCE, FHA and PRN and other known anti-pertussis mucosal antibodies) are relational to protection against colonization (BPZE1, BPZE1 + Boostrix, BPZE1 and BPZE1 + Boostrix, Boostrix control).
- To measure BPZE1 induction of mucosal immunity (S-IgA) at Day 113 by treatment group; and to assess if induction of a boost response (relative to Day 85 response) is observed for those subjects with prior BPZE1 vaccination (BPZE1, BPZE1 + Boostrix).
- To assess if Day 113 response and longer-term durability through Day 169/EOS (absolute GMT) is altered with re-vaccination/attenuated challenge when compared to those subjects who did not participate in the substudy, relative to each randomized treatment group (BPZE1, BPZE1 + Boostrix, Boostrix).

2.3.2. Serum Immunogenicity (Optional Substudy Only)

- To measure BPZE1 induction of serum immunity at Day 113; and to assess if induction of a boost response (relative to Day 85 response) is observed for those subjects with prior BPZE1 vaccination (BPZE1, BPZE1 + Boostrix).

- To assess if Day 113 response and longer-term immune durability through Day 169/EOS is altered with re-vaccination/attenuated challenge when compared to those subjects who did not participate in the substudy, relative to each randomized treatment group (BPZE1, BPZE1 + Boostrix, Boostrix).
- To assess if serum immunity of individual and combinations of pertussis antibodies (eg, WCE, PT, FHA, PRN, and other known anti-pertussis antibodies) at Day 29 or 85 is relational to protection against colonization by treatment group and overall (BPZE1, BPZE1 + Boostrix, Boostrix).
- To assess functional antibody response by treatment group at Day 113 compared to baseline and Day 29, as measured by an appropriate assay for bactericidal activity.

2.3.3. Colonization (Optional Substudy Only)

- To demonstrate prior vaccination with BPZE1 substantially reduces colonization at Days 92 and Day 99

2.3.4. Other Exploratory Objectives

- To assess cellular-mediated response (by ELISpot or flow cytometry) to BPZE1 and Boostrix (Th1 and Th2) in a subset of subjects.
- To further characterize mucosal and serum immunological responses over time, relative to baseline status and to vaccination response, with any future assays developed for BPZE1.

3. Investigational Plan

3.1. Overall Study Design and Plan

This is a multi-center, randomized, observer-blinded, placebo- and active comparator-controlled trial with a 6-month safety follow-up after first study vaccination. After signing the informed consent form (ICF; or provide assent when necessary) and meeting all inclusion and none of the exclusion criteria, eligible subjects will receive an intranasal vaccination with either BPZE1 vaccine or formulation buffer (placebo) via the MAD and an intramuscular (IM) injection of either Tdap vaccine (i.e., Boostrix) or sterile normal saline (placebo) on Day 1. To maintain the blind, placebo vaccination via intranasal and IM routes, using formulation buffer and normal saline, respectively, will be included, and an unblinded team will manage vaccine logistics, preparation, and administration (when needed to maintain blinding) but will not be involved in study related assessments or have subject contact for data collection after study vaccination.

Nasal and blood samples for immunogenicity assessments will be collected before vaccination and at selected time points following study vaccination. Mid-turbinate/nasopharyngeal sample collections will occur at selected time points following study vaccination to assess initial colonization (safety lead-in cohort only, Day 8) and to assess for clearance (remainder of cohort, either Day 29 or Day 85). A subset of subjects will also have the option to provide extra blood for cellular-mediated immunity assessments at baseline and Day 8 (safety lead-in cohort) and Days 85 and 113 (subgroup optional in substudy).

Approximately 360 subjects will be enrolled and randomly assigned (1:1:1) to 1 of 3 treatment groups (refer to [Table 3-1](#)) to contribute to safety and efficacy assessments. Enrollment will be operationally managed at the study level to maintain a minimum number of subjects enrolled in 2 age groups: 6 to 10 years, inclusive; and 11 to 17 years, inclusive. It is estimated that a 10% dropout rate will occur, allowing for approximately 108 evaluable subjects per treatment group.

Table 3-1 Dosing Scheme

Treatment Group	n	Intranasal Vaccination ^a (Day 1)		IM Vaccination ^b (Day 1)	
		BPZE1	Placebo	Boostrix	Placebo
A	120	X	-	-	X
B	120	X	-	X	-
C	120	-	X	X	-

Abbreviation: IM, intramuscular.

^a Intranasal application of ~0.4 mL per nostril (0.8 mL total volume delivered). Intranasal vaccination will occur prior to IM vaccination.

^b IM injection of 0.5 mL to the deltoid region.

All subjects will be monitored for at least 30 minutes after final study vaccination. On Day 1, intranasal vaccination will occur prior to IM vaccination with a minimum of 10 minutes (minimum of 30 minutes for subjects in the safety lead-in cohort of 11 to 17 year olds) between intranasal and IM vaccinations. Immediate reactogenicity will be assessed at 30 minutes (+30 minutes) after the last study vaccination of the Day (ie, after IM vaccination on Day 1, after nasal vaccination on Day 85), prior to release from clinical observation.

All subjects will record maximum daily reactogenicity in a subject diary for 7 consecutive days starting the day following any study vaccination (retrospective of the highest value in the previous 24 hours).

As this is the first study of BPZE1 in school-age children, a staggered enrolment is planned. The first 45 subjects enrolled will be in the older age group (11 to 17 years, inclusive) and designated the safety lead-in cohort. Reactogenicity will be reviewed with these subjects during a supplemental visit 7 days following first study vaccination. After reactogenicity for the safety lead-in cohort is reviewed by the medical monitor, medical lead, and Safety Monitoring Committee (SMC) chairman (with appropriate consultation with investigators, if needed), the remainder of subjects will be enrolled.

Due to the uncertainty with movement and/or isolation practices associated with the COVID-19 pandemic, telemedicine and remote sampling may be initiated with proper investigator and/or medical oversight.

The primary database lock will occur after all data are clean and all planned study procedures through Day 169/EOS (6 months) are complete. An interim database lock will occur after all subjects have completed Day 29 and sample testing for all primary and select secondary immune endpoints have been completed (mucosal and serum), but results will only be provided at treatment assignment level to maintain the blind. The site and those interacting directly with the site or subject data (eg, contract research organization [CRO], laboratories) will remain blinded to subject assignment until EOS or end of sample testing, depending on the activities of the associated entities.

There is an optional open-label substudy in which enrolled subjects may elect to participate at any time from the day of enrolment through Day 85. A separate signed ICF (and separate assent when necessary) will be obtained prior to participation in the substudy. Subjects will be excluded from participating in the substudy if they meet additional exclusion criteria listed in Protocol Section 4.1.2.1. Temporary vaccination holding criteria are to be followed for the Day 85 vaccination.

Up to 120 enrolled subjects may participate in the substudy. The duration of the entire study will not change; however, additional visits/procedures starting on Day 85 will include the following:

- 3 additional visits (Days 92, 99, and 113)
- 1 additional intranasal vaccination (Day 85)
- Up to 3 additional nasal samples, including 2 of those needed for midturbinate/nasopharyngeal sample collection (Days 92 and 99) and 1 needed for leukosorb (Day 113). Subjects will contribute to all Day 85 sampling (systemic and nasal).
- Up to 2 additional blood samples (Days 85, if not already assigned to provide, and 113, including blood for cellular-mediated and systemic immunity responses)
- 1 additional subject diary (subjects to record maximum daily reactogenicity [nasal/respiratory, systemic] in a subject diary for 7 consecutive days starting the day following study vaccination)
- 1 additional test for SARS-CoV-2 within 72 hours prior to Day 85 vaccination.

All subjects participating in the open-label substudy will receive an intranasal re-vaccination/attenuated challenge with BPZE1 on Day 85. Subjects may have the planned re-vaccination/attenuated challenge deferred to a later date (up to 20 days) if pre-defined temporary exclusion criteria in Protocol Section 4.1.2.1 are met or for other personal reasons (eg, holiday, school schedule). Subjects will be monitored for at least 30 minutes after re-vaccination/attenuated challenge, with a post-vaccination evaluation for reactogenicity (nasal/respiratory, and systemic) completed prior to release from clinical observation.

Subjects will receive a subject diary on Day 85. All subjects (with assistance when needed) will record maximum daily reactogenicity in a subject diary for 7 consecutive days starting the day following re-vaccination/attenuated challenge (retrospective of the highest value in the previous 24 hours).

Nasal and blood samples for immunogenicity assessments will be collected before re-vaccination/attenuated challenge and at selected time points thereafter.

Mid-turbinate/nasopharyngeal sample collections will be performed at selected time points to assess BPZE1 colonization (*B. pertussis* culture or PCR). Some subjects participating in the substudy may also provide extra blood (optional) for cellular-mediated immunity assessments on Day 85 and Day 113 (optional extra blood collection for up to 45 substudy participants).

All AEs will be monitored through 28 days after any study vaccination; all MAAEs will be monitored through 84 days following any study vaccination; and all AESIs and SAEs will be monitored through Day 169/EOS. For the substudy, all AEs will be collected following

re-vaccination/attenuated challenge on Day 85 through Day 113. Following Day 113, only MAAEs, AESIs, and SAEs will be collected through Day 169/EOS.

3.2. Study Endpoints

3.2.1. Primary Endpoints

Immunogenicity

- GMFR of BPZE1 induction of mucosal S-IgA against WCE at Day 29 by treatment group (BPZE1, BPZE1 + Boostrix).

Safety

- Occurrence of solicited AEs including local, nasal/respiratory, and systemic reactogenicity events through 7 days following first study vaccination with any combination of pertussis-containing vaccines.

3.2.2. Secondary Endpoints

3.2.2.1. Key Secondary Endpoint

- BPZE1 + Boostrix induction of serum IgG against diphtheria, tetanus, and all aP antigens (PT, FHA, PRN) compared with Boostrix at Day 29 (criteria to be assessed for diphtheria and tetanus responses per WHO guidelines).

3.2.2.2. Colonization (Optional Substudy Only)

- Proportion of subjects with colonization at either Day 92 or 99 (*B. pertussis* culture or polymerase chain reaction [PCR]) with prior BPZE1 immunization following re-vaccination/attenuated challenge at Day 85 (BPZE1, BPZE1 + Boostrix, BPZE1 and BPZE1 + Boostrix, Boostrix control).

3.2.2.3. Mucosal Secretory Immunogenicity

WCE, FHA, PRN, and any additional anti-pertussis mucosal antibodies identified during assay development using geometric mean concentration titre (GMT) and geometric mean fold rise (GMFR) unless otherwise stated.

NOTE: To also be tested separately in subjects who participate in the optional substudy as exploratory endpoints, to assess response following re-vaccination/attenuated challenge.

- BPZE1 induction of mucosal S-IgA against WCE compared with Boostrix at Day 29
- BPZE1 induction of mucosal S-IgA at Day 29 compared to baseline.
- BPZE1 and BPZE1 + Boostrix induction of mucosal S-IgA compared with baseline at Days 85 and 169/EOS (tested independently).
- BPZE1 + Boostrix induction of mucosal S-IgA compared with BPZE1 at Days 29 and 169/EOS (tested independently).
- BPZE1 and BPZE1 + Boostrix induction of mucosal S-IgA in covariate analysis by age, time since last aP vaccination (prior to study entry), or other baseline demographics at Day 29.

- BPZE1 and BPZE1 + Boostrix induction of mucosal S-IgA by baseline quantile at Day 29.
- Seroconversion rate (2-fold increase over baseline value or a 4-fold increase over the lower limit of assay detection [whenever the baseline value falls below the lower limit of assay detection]) for mucosal S-IgA at Day 29 by treatment group.
- Reverse cumulative distribution curves of each anti-pertussis mucosal antibodies S-IgA GMT at Day 29 by treatment group.

3.2.2.4. Serum Immunogenicity

WCE, PT, FHA, PRN, and any additional anti-pertussis antibodies identified during assay development using GMT and GMFR unless otherwise stated.

- BPZE1 and BPZE1 + Boostrix induction of serum immunity (IgA, IgG) at Day 29 compared with baseline (tested independently by treatment group).
- BPZE1 + Boostrix induction of serum immunity (IgA, IgG) compared with Boostrix at Day 29.
- BPZE1 and BPZE1 + Boostrix induction of serum immunity (IgA, IgG) at Day 85 and Day 169/EOS compared with baseline (tested independently by treatment group and day).
- Antibody decays (IgA, IgG) over the course of the study (tested independently by treatment group).
- BPZE1 induction of serum IgA compared with Boostrix at Day 169/EOS.
- BPZE1 + Boostrix induction of serum IgA compared with Boostrix at Day 169/EOS.
- BPZE1, BPZE1 + Boostrix, and Boostrix induction of serum immunity (IgA, IgG) by age, time since last aP vaccination (prior to study entry), or other baseline demographics at Day 29 (tested independently by treatment group).
- BPZE1, BPZE1 + Boostrix and Boostrix induction of serum immunity (IgA, IgG) at Day 29 by baseline quantile (tested independently by treatment group).
- BPZE1 and BPZE1 + Boostrix induction of measurable functional antibody (subset of subjects) compared with Boostrix at Day 29 (tested independently by treatment group).
- Seroconversion rate for serum immunity (IgA, IgG) defined as a 2-fold increase over baseline value; or a 4-fold increase over the lower limit of assay detection (whenever the baseline value falls below the lower limit of assay detection) at Days 29 and 85 (tested independently by treatment group and day).
- Reverse cumulative distribution curves of GMT at Day 29 by treatment group.

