7.4.3.2 Analyses of Secondary Serum Immunogenicity (IgA and IgG) Endpoints

All analyses will use the approaches outlined in Section 7.4.1.1 for the primary analyses, in Section 7.4.2 for the key secondary analyses and those outlined in Section 7.4.3.1 for secondary analyses.

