8.3.2. Analyses of Secondary Serum Immunogenicity (IgA and IgG) Endpoints

Descriptive responses (GMC [also known as GMT per protocol], GMFR, seroconversion) of IgA and IgG against WCE, PT, FHA, PRN, and any additional anti-pertussis antibodies identified during assay development will be conducted at each time point and by treatment group.

To test the hypothesis that BPZE1 and BPZE1 + Boostrix can induce significantly greater serum immunity (IgA, IgG) at Day 29 than baseline, separate paired t-tests will be used to compare the natural log-transformed GMC at Day 29 with the natural log-transformed GMC at baseline within each treatment group. The corresponding 95% CIs will be calculated on the natural log scale, then both lower and upper limits will be exponentiated to get the 95% CIs on the original scale.

A non-inferiority hypothesis will be tested to demonstrate BPZE1 + Boostrix induction of serum IgA is non-inferior to Boostrix at Day 29. An ANCOVA model that includes baseline IgA and treatment group as covariates will be used to compare the natural log-transformed GMCs at Day 29 between BPZE1+Boostrix and Boostrix groups. The non-inferiority margin is set at a 2-fold decrease or -0.693 on natural log scale. Non-inferiority will be demonstrated if the lower limit of the 95% CI of group difference on natural log scale is greater than -0.693.

To test the hypotheses that BPZE1 and BPZE1 + Boostrix can induce significantly greater serum immunity (IgA, IgG) at Day 85 and Day 169/EOS than baseline, separate paired t-tests will be used to compare the natural log-transformed GMC at Day 85 and Day 169/EOS with the natural log-transformed GMC at baseline within each treatment group. The corresponding 95% CIs by treatment group and day will be calculated on the natural log scale, then both lower and upper limits will be exponentiated to get the 95% CIs on the original scale.

The non-inferiority hypothesis will be tested to demonstrate: 1) BPZE1 induction of serum IgA and IgG is non-inferior to Boostrix at Day 85 and Day 169/EOS; 2) BPZE1+ Boostrix induction

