of serum IgA and IgG is non-inferior to Boostrix at Day 85 and Day 169/EOS. An ANCOVA model that includes baseline IgA or IgG and treatment group as covariates will be used to compare the natural log-transformed GMCs at Day 85 and Day 169/EOS between either BPZE1 or BPZE1+Boostrix and Boostrix groups. The non-inferiority margin is set at a 2-fold decrease or -0.693 on natural log scale. Non-inferiority will be demonstrated if the lower limit of the 95% CI of group difference on natural log scale is greater than -0.693.

Subgroup analysis by age group (6-10 years and 11-17 years, inclusive, and 10 – 17 years [for requested analyses]), time since last aP vaccination prior to study entry (<median time, \geq median time), or other baseline demographics, and by baseline antibody level (by quantile) will be conducted to examine differential responses to induction of serum immunity (IgA, IgG) at Day 29 by treatment group (BPZE1, BPZE1+Boostrix, and Boostrix). In addition to descriptive summaries, a forest plot of the corresponding 95% CIs will be generated for each subgroup.

To compare BPZE1 and BPZE1 + Boostrix induction of measurable functional antibody (subset of subjects) with Boostrix at Day 29, separate two-sample t-tests will be used to compare between treatment group differences in natural log-transformed GMC at Day 29. The corresponding 95% CIs by treatment group will be calculated on the natural log scale, then both lower and upper limits will be exponentiated to get the 95% CIs on the original scale.

Seroconversion rates with 95% CIs for IgA and IgG will be calculated at Days 29 and 85 by treatment group and day. The 95% CI will be calculated by using Agresti-Coull method. The likelihood ratio chi-square test will be used to compare seroconversion rate between treatment groups. Additional combinations of antibody response (WCE, PT, FHA, PRN, and any additional anti-pertussis antibodies) may also be tested.

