8.4.3. Analysis of Serum Immunogenicity Endpoints

To test the hypothesis that BPZE1 induction of serum immunity (IgA, IgG) at Day 113 compared with baseline, or Day 113 compared with Day 85, separate paired t-tests will be used to compare the natural log-transformed GMC at Day 113 with the natural log-transformed GMC at either baseline or Day 85 within each treatment group (BPZE1, BPZE1 + Boostrix, Boostrix). The corresponding 95% CIs will be calculated on the natural log scale, then both lower and upper limits will be exponentiated to get the 95% CIs on the original scale.

BPZE1, BPZE1 + Boostrix, and Boostrix induction of serum immunity (IgA, IgG) at Day 113 and Day 169/EOS will be summarized by participation in the substudy (Yes/No) and by treatment group and by timepoint. Separate two sample t-tests will be used to compare the natural log-transformed GMCs at Day 113 and Day 169/EOS between subjects who participated in the substudy and subjects who did not participate in the substudy (Day 169/EOS only), by treatment group and by timepoint.

BPZE1, BPZE1+Boostrix, BPZE1 and BPZE1+Boostrix, Boostrix control induction of serum immunity (IgA, IgG) at Days 29 and 85 will be summarized by protection against colonization (colonized/non-colonized) and by treatment group and by timepoint. Comparison between colonized subjects and non-colonized subjects will be made using separate two-sample t-tests by treatment group and by timepoint.

The number and proportion of subjects with $\geq 50\%$ killing titer (or equivalent) at Day 113 compared to baseline and Day 29 will be summarized by treatment group and by timepoint. The 95% CI will be provided by using Agresti-Coull method. A McNemar test will be used to compare proportions between timepoints in each treatment groups (Day 113 vs baseline; Day 113 vs Day 29).

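### The secondary endpoint of serum antibody decay has no analysis that estimates or tests decay, and Day 169 summaries can include children re-dosed with BPZE1 at Day 85

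*SAP*

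**What the plan says.** SAP 3.2.2.4 lists the endpoint "Antibody decays (IgA, IgG) over the course of the study (tested independently by treatment group"). The objective in SAP 2.2.4 is "to assess antibody decay curves for BPZE1, BPZE1 + Boostrix and Boostrix". Protocol 2.2 carries the same objective and endpoint.

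The methods provide the following for serum IgA and IgG:

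- Within arm (SAP 8.3.2): paired t-tests that "compare the natural log-transformed GMC at Day 85 and Day 169/EOS with the natural log-transformed GMC at baseline within each treatment group", and the same at Day 29. The stated hypotheses name the two BPZE1 arms, not Boostrix.
- Between arms (SAP 8.3.2): ANCOVA non-inferiority models that "compare the natural log-transformed GMCs at Day 85 and Day 169/EOS between either BPZE1 or BPZE1+Boostrix and Boostrix groups", and one for IgA at Day 29. The key secondary IgG comparisons at Day 29 (SAP 8.2) are also between arms.
- Substudy (SAP 8.4.3): paired t-tests that "compare the natural log-transformed GMC at Day 113 with the natural log-transformed GMC at either baseline or Day 85 within each treatment group", and a comparison of participants with non-participants at Day 169.
- Description (SAP 8.3.2): GMC, GMFR and seroconversion, which "will be conducted at each time point and by treatment group". SAP section 4 extends these summaries to all subjects and adds a separate post-Day-85 analysis for the substudy.

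Protocol 7.4.3.2 adds no method of its own: "All analyses will use the approaches outlined in Section 7.4.1.1 for the primary analyses", with further cross-references to 7.4.2 and 7.4.3.1.

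**The concern.** The endpoint is worded as something to be tested in each arm, yet the methods never mention a decay rate, slope, half-life or repeated-measures model, nor a contrast of Day 29 with a later day. Being above baseline at Day 169 shows that some response persists. It does not show how much of the Day 29 response has been lost, so slow and fast waning can give the same test result.

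The fallback is to read decay from GMCs by visit, and that has its own weakness. Up to 120 enrolled children receive a BPZE1 dose at Day 85, in every arm. The per-protocol immunogenicity set (SAP 4.3.4) does not remove samples taken after that dose, and the note to the serum endpoints in Protocol 2.2 makes the separate substudy testing an addition. A Day 169 summary over all subjects can thus mix children who had one vaccination day with children who had two.

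At stake is a stated secondary question: how fast serum antibody wanes after BPZE1, with and without Boostrix, relative to Boostrix alone.

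**Working it through.** The documents give no sample size, power or precision for decay, so there is no stated figure to reproduce. The SDs borrowed in step 4 come from SAP Table 4-2. With 108 per arm and a noncentral t they return powers of 97.0% (PT), 100% (FHA) and 88.3% (PRN), against 97.0%, 100% and 88.2% stated.

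**1. Classify the planned serum tests by contrast.**

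| Test | Contrast | Measures decay? |
|---|---|---|
| SAP 8.3.2 paired t, Days 29, 85, 169 | visit against baseline | no |
| SAP 8.2 and 8.3.2 ANCOVA, Days 29, 85, 169 | arm against arm at one visit | no |
| SAP 8.3.2 functional antibody, seroconversion, seropositivity | arm against arm at one visit | no |
| SAP 8.4.3 paired t | Day 113 against baseline or Day 85 | no: Day 113 follows the Day 85 dose |
| SAP 8.4.3 McNemar, bactericidal killing | Day 113 against baseline or Day 29 | no: Day 113 follows the Day 85 dose |
| SAP 8.4.3 two-sample t | participants against non-participants, Day 169 | no |
| SAP 8.4.3 two-sample t | colonised against not, Days 29 and 85 | no |

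No main-study serum test contrasts two post-vaccination days within an arm.

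**2. Why a test against baseline does not measure decay.** Suppose two arms both have a GMFR of 2.0 at Day 169, one falling from 2.5 at Day 29 and the other from 12. With 108 subjects and an assumed SD of 0.8759 for the log difference, the Day 169 test has power above 99.9% in both. With log-linear decay over 169 − 29 = 140 days, half-life = 140 × ln 2 / ln(GMFR29/GMFR169):

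- 2.5 to 2.0: ratio 0.80, half-life 140 × 0.693 / 0.223 = about 435 days.
- 12 to 2.0: ratio 0.17, half-life 140 × 0.693 / 1.792 = about 54 days.

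**3. Effect of including re-dosed children at Day 169.** Let p be the share re-dosed and b the boost still present at Day 169. The documents do not give b, so it is assumed. For a true 90-day half-life, the log fall over Days 85 to 169 (84 days) is 84 × ln 2 / 90 = 0.647. The all-subjects mean falls by 0.647 − p × ln b, and the apparent half-life is 84 × ln 2 divided by that fall.

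- b = 1 (no residual boost), any p: 58.2 / 0.647 = 90 days.
- b = 2, p = 120/360 = 1/3: 58.2 / (0.647 − 0.231) = 58.2 / 0.416 = about 140 days.
- b = 2, p = 1/6 (half that uptake): 58.2 / (0.647 − 0.116) = 58.2 / 0.531 = about 110 days.

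**4. Can the planned data support a decay contrast?** For a within-arm Day 169/Day 29 ratio, the SD of the log difference is SD × √(2(1 − ρ)), and the CI factor is exp(t × SD of difference / √n). The within-subject correlation ρ is not in the documents; 0.5 to 0.9 is assumed, and the Table 4-2 SDs are applied to both days. If the substudy fills and splits evenly, 120 − 40 = 80 per arm remain, or 72 after 10% dropout.

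| n per arm | PT, CI factor (ρ 0.5 to 0.9) | PRN, CI factor (ρ 0.5 to 0.9) |
|---|---|---|
| 108 | 1.18 to 1.08 | 1.32 to 1.13 |
| 72 | 1.23 to 1.10 | 1.40 to 1.16 |

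Worked case (72, PT, ρ = 0.5): exp(1.994 × 0.8759 / √72) = exp(0.206) = 1.23. The contrast is feasible without the re-dosed samples.

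**The case against.** A reader might infer that every planned serum test is against baseline. The documents do not support that: the ANCOVA models compare arms at Days 29, 85 and 169, and the substudy compares Day 113 with Day 85.

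A reader might also infer that durability by arm cannot be answered at all. That is too strong. GMC and GMFR with 95% CIs are planned by arm and visit, and SAP 8.3 makes summaries the default for listed endpoints. The objective speaks of assessing curves, and visit-wise GMCs do draw a curve. Persistence above baseline is tested. The half-lives in step 2 come from GMFRs that the plan will report.

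Further points carry weight. The generic paired t-test for two time points in Protocol 7.4.3.1, which 7.4.3.2 extends to serum, gives baseline only as an example and could be applied to Day 169 against Day 29. SAP 8.4.3 summarises Day 169 by substudy participation, so an unboosted Day 169 GMC should be available. Lead-in children who may skip sampling are at most 45 of about 360 (12.5%), and only at Day 85. The 140-day figure needs maximum uptake and a lasting 2-fold boost.

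What remains is that neither document names a decay contrast, although the endpoint is to be tested. Applying the generic test would mean choosing days, subjects and handling of re-dosed children without pre-specification, in a SAP whose stated purpose is pre-specification. The summaries give no CI for the fall between visits, and the main Day 169 summary is not said to exclude re-dosed children.

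**Conclusion.** The concern holds as a gap in specification with a possible bias attached. The decay endpoint has no planned estimate or test, and the fallback summaries can include up to one third of children re-dosed at Day 85.

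The direction of bias is towards slower decay, provided the re-dose raises serum antibody. Its size ranges from nothing (no residual boost) to a 90-day half-life read as about 140 days (2-fold residual boost, full uptake, even split across arms), with about 110 days at half uptake. These are illustrations; the documents give neither the residual boost nor the actual uptake.

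This is a secondary endpoint outside the key secondary family, with no power claim and no success criterion. The primary and key secondary analyses rest on Day 29 and are not affected.

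**What to change.** Add a paragraph to SAP 8.3.2. For each isotype and antigen and each of the three arms, report the within-subject Day 85/Day 29 and Day 169/Day 29 GMC ratios with 95% CIs, and the difference in log-ratio of each BPZE1 arm from Boostrix. Exclude every sample taken after a Day 85 BPZE1 dose. Day 85 samples from substudy children stay in, since they are to be drawn before re-dosing.

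An alternative is a repeated-measures model of ln concentration by actual sampling day. It accommodates lead-in children without a Day 85 sample and the wide analysis windows in SAP 4.5 (Days 19 to 57, 58 to 127 and 128 to 199 in the main study). Report decay rates by interval, and a half-life only where the CI for the slope excludes zero.

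The cost is one paragraph and one set of tables, on samples already in the schedule. There are two downsides. Fewer children contribute at Day 169, about 72 per arm if the substudy fills and splits evenly. Because children opt in to the substudy, those who remain may be a selected group, so their baseline and Day 29 values should be shown beside those of participants.
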